### 13.3 Go/No-go Milestones, Challenges and Opportunities

Our systematic approach to building the study's main tele-health assessment platforms and then sequentially recruiting its sub-cohorts suggests realistic prospects of meeting our project timeline and of reaching pivotal Go/No-go milestones set at 75% of recruitment and retention goals to ensure a reasonable likelihood of accomplishing our SAs. However, in the event that a milestone was not achieved then NINDS program staff would determine in discussion with the SC whether the study should be continued and/or adapted.

Just as our infrastructure plans (under SA1) rely on logistical capabilities, our experimental hypotheses (under SAs 2 and 3) depend on scientific assumptions, which if challenged would lead us to consider contingencies accordingly. For example, the ability to compare disability progression measured by tele-health platforms relies on true disease progression during two years of cohort follow up. However, this period coincides with the so-called 'honeymoon' phase of treatment after DT initiation when observable motor progression may be modest due to early, uncomplicated medication titration (40). Anticipating this possible pitfall, we will incorporate an adjustment for levodopa dose equivalents in our motor score-based progression analysis. We will also explore dopa-resistant cognitive outcomes and would proactively consider options to further extend the cohort into subsequent phases of non-motor and dopa-resistant disability accumulation. In addition, we will remain open to new opportunities to leverage the project's resources; for example, adopting potentially more sensitive wearable technologies in this rapidly evolving mobile health field, or assessing events to which the study cohort may be uniquely suited such as the impact of parent trial results, which should be announced during the follow-up period.

#### 13.4 Sample Size Determination

SA 1b. With a sample size of ~10 SURE-PD3 and ~50 SUPER-PD participants expected to complete at least one TV close in time to their in-person clinic visit, the study will have 80% power to conclude that the REACT-PD calibrated tele-visit estimates are sufficiently accurate ( $r_c > 0.8$  at  $\alpha = 0.05$ ) if the true concordance is at least 0.89.

SA 2a. With a 2:1 split of ~340 AT-HOME PD participants, yielding ~115 participants contributing to validation tests, the study will have 80% power to declare a given SP measure sufficiently accurate ( $r_c > 0.80$  at  $\alpha = 0.05$ ) if the true concordance is at least 0.87.

SA 2b. With approximately 80% of participants participating in the SP portion of the study, yielding ~340 participants contributing to the smartphone vs tele-visit comparison, the study would have an 80% probability of selecting the true preferred measure from a pair of TV or SP if the preferred measure had lower standard error by an effect size of at least 0.065.

SA 3. With a 2:1 split of ~240 participants, yielding ~80 in the validation sample and at least 25% experiencing at least an 8-point progression in MDS-UPDS parts 1-3 total score, the study would have 80% power to

declare a novel measure derived from passive SP monitoring to have a ROC AUC significantly greater than 0.80 if the true AUC were at least 0.95.

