Data Management	
Data collected during tele-visits will be entered and maintained in REDCap (a secure web-based survey and data management system). Each participant’s baseline demographic information, concomitant medications, and health history as well as clinical data including PD-PROP from the corresponding SUPER-PD visit, will be transferred from the SUPER-PD REDCap project to the AHPD sub-study REDCap project. All data will ultimately be transferred to Synapse (an open source collaborative platform) for analysis. For any sub-study participants who are participating in the mPower 2.0 component of SUPER-PD, their smartphone data from the corresponding SUPER-PD visit and associated remote 2-week burst will be linked with AT-HOME PD data within Synapse.
 
From Synapse, the cleaned, processed, and event date- and time-transformed dataset will be transferred to the PDBP’s Data Management Resource for further distribution to PDBP investigators and will be made available to the wider research community through their qualified researchers program.

Statistical Analysis	Paired MDS-UPDRS and MoCA scores from in-person and TV assessments of SUPER-PD participants will be pooled with data from SURE-PD3. The accuracy of predicted in-clinic scores based

	
on TV assessments using calibrations from REACT-PD will be summarized by Lin's concordance correlation coefficient, <math>r_c</math>, equivalent to an intra-class correlation (ICC). The REACT-PD calibrations will be judged sufficiently accurate if <math>r_c > 0.8</math>. If we observe insufficient concordance, we will re-calibrate using all available data from REACT-PD, SURE-PD3, and SUPER-PD.

Sample Size	
With a combined sample size of ~60 SURE-PD3 and SUPER-PD participants expected to complete at least one TV close in time to their in-person clinic visit, the study will have 80% power to conclude that the REACT-PD calibrated tele-visit estimates are sufficiently accurate (<math>r_c > 0.8</math> at alpha = 0.05) if the true concordance is at least 0.89.

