## 4. STUDY POPULATION

### 4.1 Participant Numbers

#### 4.1.1 AT-HOME PD Participants

Approximately 420

All individuals with early idiopathic PD enrolled in the STEADY-PD III (NCT02168842) and SURE-PD3 (NCT02642393) studies (N~600) who have consented to be contacted for future research will be asked to participate. We expect approximately 70% of them (N~420) to consent and participate in at least the tele-visit portion of the study. We expect approximately 80% of enrolled individuals (N~340) to participate in the smartphone portion (and thus the smartphone vs tele-visit comparison) of the study. We expect approximately 70% of participants in the smartphone portion (N~240) to consent to passive data collection (and thus contribute to Aim 3). We expect approximately 80% of enrolled individuals (N~340) to participate in the FI portion of the study.

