If AT-HOME PD study participants will be considered for any future follow up research their contact information will be obtained from the University of Rochester (UR) secure HIPAA compliant database based on original consent. If the subject declined contact in the original study, the subject will be allowed to contact the UR AHPD study team directly with an interest in study participation.

Considering the low participant burden of remote data collection, an inherent advantage of the outcome measures under investigation, we anticipate a modest dropout rate of ~15% from the tele-visit component over the two-year extension study. In addition, recruitment and retention will be motivated by multiple tested strategies ranging from reasonable reimbursement payments (to be paid in three installments following each tele-visit via check) to regular communication with participants.

Formative research through patient interviews indicates that long-term data collection in a remote setting will only be sustainable with a smartphone application that is specifically designed to meet the needs and interests of the participant population. Based on initial interviews, engagement strategies will focus on altruism, self-exploration, education, and community. These are implemented through the application using news feeds, infographics, participation dashboards, and notifications. Importantly, participants will be provided with the option to view the outcomes of their assessments in a manner that was highly effective at promoting engagement within mPower but was not feasible during the smartphone sub-study (Smart4SURE) of SURE-PD3.

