***Aim 3:***

We will evaluate the feasibility to collect and use passive data to track disease progression. Passive data collection will come in two flavors - displacement tracking that captures a participant's life space, i.e. their mobility patterns and collection of accelerometer and gyroscope readings when the participants are walking throughout the day. The walking data will be analyzed exactly the same as the actively collected data as described in Aim 2. The displacement tracking requires more care and will require us to first determine feasibility of data collection (Aim 3a) and extensive norming before assessing ability to track progression (Aim 3b).

Evaluation of Data Collection:

The first component of this Aim will focus on evaluating the feasibility of collecting passive data from individuals over a 2- year time period. This includes addressing two potential barriers to data collection: (1) Participant willingness to provide permission for passive monitoring and (2) the ability to collect passive data continuously over a 2-year period despite infrastructure changes caused by smartphone hardware and software upgrades.

*Hypothesis:* 70% of AT-HOME PD participants who participate in the smartphone component will consent to collection of passive data.

This will be evaluated by observing the number of active participants willing to enroll in this sub-study.

*Hypothesis:* Passive data will be collected in a persistent manner for the full 2-year study in at least 75% of consented individuals. Data collection will be monitored on a continuous basis.

We will evaluate the ability to use passive motor measures to predict relative changes in disease severity within a participant. Due to the highly individualized nature of activity patterns, it is unknown whether passive data can be used to derive absolute measures of disease severity. However, we expect that relative changes in activity patterns over time will provide a mechanism to track disease progression on an individualized basis. Features from displacement data such as total daily movement, number of daily trips, etc. will be generated and normed per individual before evaluation of disease progression using the same methods as described in SA 2b.

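### The SA 3 power statement counts all ~80 people in the validation split as having a progression outcome, with no allowance for the ~15% tele-visit dropout the plan expects

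*Combined protocol and SAP*

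**What the plan says.** Section 4.1.1 gives the source of the SA 3 sample: "We expect approximately 70% of participants in the smartphone portion (N~240) to consent to passive data collection". Section 13.4 starts from that number, "With a 2:1 split of ~240 participants", "yielding ~80 in the validation sample and at least 25% experiencing at least an 8-point progression" on the MDS-UPDRS parts 1-3 total. It claims 80% power to show a "ROC AUC significantly greater than 0.80 if the true AUC were at least 0.95". The Synopsis repeats the statement.

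Two other places forecast losses. Section 5.1 (Recruitment) says "we anticipate a modest dropout rate of ~15% from the tele-visit component over the two-year extension study". Section 13.2, Aim 3, sets the hypothesis that "Passive data will be collected in a persistent manner for the full 2-year study in at least 75% of consented individuals".

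The SA 3 statement gives no alpha, sidedness, AUC test or variance formula, and no time horizon for the 8-point change. SA 1b and SA 2a do state alpha 0.05.

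**The concern.** Consent to passive collection does not by itself produce an SA 3 data point. The outcome needs a baseline score and a later tele-visit score, and the predictor needs passive data over the period. The plan expects to lose some of both, yet the power statement deducts nothing.

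The effective sample size for an AUC is driven by the smaller group, here the progressors. The stated design has only 20 of them, so losing a few matters. This is the only power statement for Aim 3, so a reader judging whether the passive-data measure can be validated has nothing else to rely on.

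**Working it through.** **Inputs.** From 13.4: 240 participants, 2:1 split, 25% progressors, null AUC 0.80, true AUC 0.95, power 80%. From 5.1: dropout 15%. From 13.2, Aim 3: persistence 75%. Assumed, because SA 3 does not say: alpha 0.05, run one- and two-sided.

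**Step 1: where the 80 comes from.** 240 / 3 = 80, with 80 x 0.25 = 20 progressors and 60 others. No loss is deducted.

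**Step 2: apply the plan's own losses.**
- Dropout only: 80 x 0.85 = 68; progressors 68 x 0.25 = 17.
- Persistence only, or dropouts nested within the non-persistent group: 80 x 0.75 = 60; progressors 15.
- Both, independent: 80 x 0.85 x 0.75 = 51; progressors about 13.

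**Step 3: try to reproduce the 80%.** I used a one-sample z-test on the AUC:

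power = Phi((0.95 - 0.80 - z x SE0) / SE1)

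SE0 is taken at AUC 0.80 and SE1 at 0.95. The Hanley-McNeil variance is

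[A(1 - A) + (n1 - 1)(q1 - A²) + (n0 - 1)(q2 - A²)] / (n1 n0), with q1 = A/(2 - A) and q2 = 2A²/(1 + A).

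At n1 = 20 and n0 = 60, SE0 = 0.0637 and SE1 = 0.0348.
- Two-sided (z = 1.960): (0.15 - 0.1248)/0.0348 = 0.725, power 76.6%. The AUC needed for 80% is about 0.953, which rounds to the plan's 0.95.
- One-sided (z = 1.645): (0.15 - 0.1047)/0.0348 = 1.30, power 90.3%.

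Neither gives 80%. None of the other forms tried (Obuchowski, exact binormal, logit-scale, simulated DeLong) came within 2 points. The nearest above were Obuchowski on the logit scale, two-sided, at 83.5% and a simulated null-SE test, two-sided, at 84.1%. The method behind the 80% therefore cannot be identified.

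The plan's other figures suggest a one-sided test. By Fisher z, SA 2a (n = 115, 0.87 against 0.80) gives 79.9% one-sided and 69.9% two-sided. SA 1b at n = 60 (0.89 against 0.80) gives 78.7% one-sided.

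**Step 4: Hanley-McNeil at the reduced sizes.**

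| Evaluable n | SE0 | SE1 | Power at 0.95, one-sided | Power at 0.95, two-sided | AUC for 80%, one-sided | AUC for 80%, two-sided |
|---|---|---|---|---|---|---|
| 80 | 0.0637 | 0.0348 | 90% | 77% | 0.937 | 0.953 |
| 68 | 0.0691 | 0.0378 | 83% | 65% | 0.947 | 0.963 |
| 60 | 0.0737 | 0.0403 | 76% | 56% | 0.954 | 0.971 |
| 51 | 0.0800 | 0.0438 | 66% | 44% | 0.963 | 0.980 |

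**Step 5: other variances, at n = 80 / 68 / 60 / 51.** Exact binormal two-sided: 94 / 85 / 76 / 63%. Exact binormal one-sided: 99 / 96 / 92 / 84%. Simulated Wald-DeLong two-sided: 98 / 96 / 94 / about 91%. Those that stay above 80% throughout start far above 80% at n = 80, so they do not explain the stated figure.

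**The case against.** A reader might infer that power falls below 80% at every size from 51 to 68. The documents do not support that. SA 3 names no test or sidedness. One-sided Hanley-McNeil, the sidedness that fits SA 1b and SA 2a, still gives 83% at 68, and some other tests exceed 80% even at 51.

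A reader might also take 51 as the number the plan leaves. That needs two things the plan does not say: that the two losses are independent, and that anyone without full two-year passive data is unusable. The 75% is a feasibility hypothesis stated as a minimum, not an evaluability rule.

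Nor is 68 a strict ceiling. Section 13.5 keeps all available data regardless of compliance, the withdrawal visit in Section 5.5 includes the MDS-UPDRS where it can be done, and there is a full month-12 tele-visit. Without a stated horizon, some dropouts could still supply an outcome. The 25% progression rate is also a minimum: at 30%, 68 people would include 68 x 0.30 = 20.4 progressors. Finally, Aim 3 is exploratory and all the counts are approximate.

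These points stand, and they limit what can be said about the size of the shortfall. They do not justify using 80 undiminished. Withdrawal visits will not always take place, keeping all available data cannot supply a score that was never obtained, and a shorter follow-up leaves less time for an 8-point change.

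**Conclusion.** The omission is established from the plan's own figures and does not depend on any power formula: the SA 3 validation size carries no allowance for a loss that Section 5.1 expects. The supportable planning number is about 68 evaluable (about 17 progressors at 25%), with about 60 if persistence is binding and 51 only as a worst case.

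Whatever method gave 80% at n = 80 must give less at these sizes. How much less cannot be fixed until the test is named. On Hanley-McNeil, a shortfall below 80% at 68 appears two-sided (65%) but not one-sided (83%). At 60 it appears on both (56% and 76%). These figures assume alpha 0.05, exactly 25% progressors and a true AUC of 0.95. Neither a fixed range of 51 to 68 evaluable nor a single replacement AUC should be read as established. The point is worth correcting, but it does not threaten the design.

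**What to change.** In Section 13.4 and the Synopsis:

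- Base the SA 3 statement on the number evaluable after the plan's own 15% dropout (~68, about 17 progressors), with ~60 as a sensitivity case for passive-data persistence. If the authors expect withdrawal-visit or month-12 scores to recover some people, say so and justify a different number.
- State alpha, sidedness, the AUC test and its variance method, and the time horizon of the 8-point change.
- Give the recomputed power or detectable AUC under that named test. If it is Hanley-McNeil, the AUC for 80% power is about 0.947 one-sided or 0.963 two-sided at 68, and about 0.954 or 0.971 at 60.

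This changes text only. No extra enrolment is needed, and the cost is a slightly less favourable stated figure.

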### 13.5 Non-Compliance, and Withdrawals

All available data will be included in the primary analyses regardless of protocol compliance. Secondary analyses may restrict the sample to participants meeting pre-specified compliance criteria.

We will summarize the proportion of eligible participants in the parent trials who enroll in AT-HOME PD and the proportion of those enrolled who (1) complete each tele-visit, (2) complete each FI quarterly assessment, (3) download and install the AT-HOME PD app, (4) complete periodic AT-HOME PD tasks, and (5) consent to passive data collection.

### 13.6 Safety Analysis

RE information collected at study tele-visits will be summarized. All participants will be included in the safety analysis. At a minimum, individual report information will be displayed, and RE rates tabulated.

## **PART B - GOOD CLINICAL PRACTICE/ADMINISTRATION**

### 14. REGULATORY/ETHICS

#### 14.1 Compliance Statement

This study will be conducted in accordance with the Good Clinical Practice (GCP) guidelines promulgated by the International Conference on Harmonization (ICH) and the FDA, and any applicable national and local regulations including FDA regulations under 21 CFR Parts 11, 50, 54, 56, 312 and 314.

All procedures not described in this protocol will be performed according to the study Operations Guide/Manual unless otherwise stated.

#### 14.2 Informed Consent

This study will be conducted in accordance with the provisions of 21 Code of Federal Regulations (CFR) Part 50. NINDS and the CHeT/CTCC must be given an opportunity to review the consent form prior to site IRB submission and before it is used in the study.

In accordance with relevant regulations, an informed consent agreement explaining the procedures and requirements of the study, together with any potential hazards/risks must be provided to each participant. Each participant will electronically sign such an informed consent form.

The proposed research poses minimal risk to participants. Waiver of documentation of consent will be sought as eConsenting is not recognized by the Office of Research and Project Administration.

The participant must be assured of the freedom to withdraw from participation in the study at any time.

It is the study team's responsibility to make sure that the participant understands what she/he is agreeing to and that informed consent is obtained before the participant is involved in any protocol-defined with the exception of those pre-screening questions. It is also the study team's responsibility to verify participant identity, verify completion of the eConsent form and participant understanding of the study.

The consent process for each participant who provides consent will be documented in the participant's electronic source record and should include the date eConsent was provided, the date participant understanding was verified by the study team, and the date of the screening visit.

#### 14.3 Institutional Review Board/Independent Ethics Committee

The study team will supply the CHeT/CTCC with all necessary information for submission of the protocol and consent form to the IRB for review and approval. The CHeT Site Investigator agrees to provide the IRB with all appropriate material. The study will not begin until the Investigator has obtained appropriate IRB approval. A copy of the approval letter listing all documents and versions that were approved and the approved electronic consent form must be placed on file at the CHeT/CTCC.

The CHeT Site Investigator will request from the IRB a composition of the IRB members reviewing the protocol and informed consent. Appropriate reports on the progress of this study by the Investigator will be made to the IRB and NINDS in accordance with institutional and government regulations. It is the CHeT Site Investigator's responsibility to notify the IRB when the study ends. This includes study discontinuation, whether it is permanent or temporary. A copy of the site IRB's acknowledgement of study completion must be filed at the CHeT/CTCC.

The CHeT Site Investigator will discuss any proposed protocol changes with the CTCC Project Manager and no modifications will be made without prior written approval by NINDS, except where clinical judgment requires an immediate change for reasons of participant welfare. The IRB will be informed of any amendments to the protocol or electronic consent form, and approval, where and when appropriate, will be obtained before implementation.

#### 14.4 Protocol Amendments

Changes to the protocol should only be made via an approved protocol amendment. Protocol amendments must be approved by the Sponsor,

the study's Steering Committee and the respective site's IRB prior to implementation, except when necessary to eliminate hazards and/or to protect the safety, rights or welfare of participants. (See Investigator's Agreement.)

#### 14.5 Participant Confidentiality

The CHeT Site Investigator must assure that the privacy of participants, including their personal identity and personal medical information, will be maintained at all times. In the U.S. there are additional privacy obligations to study participants under the Health Insurance Portability and Accountability Act (HIPAA). Participants will be identified by code numbers on case report forms and other documents.

After a participant agrees to study participation via an eConsent form, it is required that the CHeT Site Investigator permit the study monitor, independent auditor or regulatory agency personnel to review the completed informed consent(s) and that portion of the participant's medical record that is directly related to the study.

The participant's authorization allows the Sponsor and CHeT/CTCC to receive and review the participants' protected health information that may be re-disclosed to any authorized representative of the Sponsor, CHeT/CTCC for review of participant medical records in the context of the study.

### 15. DOCUMENTATION

#### 15.1 Investigator Site File

As part of the Trial Master File, the CHeT Site Investigator should have the following study documents accessible for review during the study.

- i. *Curriculum vitae* for investigator and staff signed and dated within 2 years of initiation of involvement in study
- ii. The signed IRB/IEC form/letter stating IRB/IEC approval of protocol, eConsent forms, and advertisement notices, documentation of the IRB/IEC composition, and all IRB/IEC correspondence including notification/approval of protocol amendments, notification of reportable events to the IRB/IEC per local reporting requirements, and IRB/IEC notification of study termination
- iii. IRB/IEC approved electronic consent form (sample) and advertisement materials
- iv. Signed protocol (and amendments, where applicable)
- v. Electronically consented and dated participant electronic consent forms will reside in the REDCap database.
- vi. Access to eCRF source records

- vii. Delegation Log with names, signatures, initials, and functional role of all persons completing protocol assessments, providing back-up to the CHeT Site Investigator and Coordinator, if applicable, as well as staff entering data to the REDCap system.
- viii. Any source data not kept within the participant's REDCap database.
- ix. Signed and dated receipt of equipment if required for the study.
- x. Record of all monitoring visits made by NINDS personnel
- xi. Copies of correspondence to and from NINDS, including all other platforms and CHeT/CTCC.
- xii. Record of any Corrective and Preventive Action Plans (CAPA) as required by the NINDS
- xiii. Certificate for Human Participant Protection Program (HSPP) training for each individual named on the Delegation Log who have direct participant contact
- xiv. Copy of professional licensure/registration, as applicable, for each individual named on the Delegation Log, who has direct participant contact ensuring licensure is in the state in which the study will be conducted
- xv. A Note to File indicating the assessments that will be considered source documents, if applicable
- xvi. Any other documentation as required by the CHeT/CTCC (e.g., Conflict-of-Interest/Financial Disclosure)

The CHeT Site Investigator must also retain all printouts/reports, which are not recorded in REDCap.

